Employees: Recruitment efforts will follow AdventHealth recruitment Standard Operating Procedures (SOPs) at AH or PBRC recruitment SOPs for research at PBRC. AdventHealth and PBRC employees will not be individually targeted nor excluded from study participation based on employment. AdventHealth and PBRC employees who engage the AdventHealth Translational Research Institute or PBRC asking to participate in the study will be processed per standard consent procedures for participants. In addition, during the consent process, the study staff will review standard consent language stating that an employee's participation or lack of participation in the study will not affect their employment status or relationship with AdventHealth or PBRC.

Students: Students will not be individually targeted nor excluded from study participation based on employment.

Inclusion Criteria

- 1. Men and pre-menopausal women;
- 2. 18-45 years of age;
- 3. BMI $30.0-40.0 \text{ kg/m}^2$;
- 4. For women, if not using pharmaceutical (hormonal) contraception (i.e. birth control pills, vaginal ring, injections, or implant), must agree to use either a double barrier method as a form of birth control to prevent pregnancy (i.e. male condom with spermicide, with or without cervical cap or diaphragm); use implants or intrauterine contraceptive devices; have a tubal ligation (surgically sterile); practice abstinence; or be in an established relationship with a vasectomized or same sex partner during the entire duration of the study;
- 5. Able to speak and understand written and spoken English;
- 6. Sedentary defined as self-reporting no more than 1 day per week, lasting no more than 60 minutes, of regular (structured) endurance or resistance exercise in the past year.
- 7. Must be willing to be randomized to either study group;
- 8. Must be willing to adhere to all study procedures.
- 9. Participant has voluntarily signed and dated an informed consent form, approved by an Institutional Review Board/Independent Ethics Committee, and provided Health Insurance Portability and Accountability Act authorization (HIPAA) or other privacy authorization prior to any participation in study.

Exclusion Criteria

- 1. Self-reported unstable body weight in the last 3 months ($>\pm5\%$);
- 2. Significant changes in the quality of the diet or the level of physical activity within the last 3 months;

- 3. Weight >396 lb (180 kg);
- 4. Diagnosis of Type 1 or Type 2 diabetes mellitus;

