- 23. Known allergy to lidocaine or other local anesthetic;

- 24. Hyperthyroidism including those with normal TSH (0.35-4.5) on pharmacological treatment; individuals with hypothyroidism may be referred to their primary care provider for evaluation and retested; any medication change for hypothyroidism must be stable for ≥ 3 months prior to retesting;
- 25. Previous bariatric or other surgery for obesity;
- 26. History of cancer (other than non-melanoma skin cancer) within the last 5 years (not in remission); anti-hormonal therapy (e.g., for breast or prostate cancer) within the last 6 months;
- 27. Diagnosed psychotic or psychiatric conditions prohibiting adherence to study protocol; hospitalization for any psychotic or psychiatric condition within one year;
- 28. Currently pregnant (pregnancy test performed on day of DEXA scan in women of child-bearing potential); post-partum during the last 12 months; lactating during the last 12 months; planning to become pregnant during the participation period;
- 29. Polycystic Ovarian Syndrome (PCOS) (self-report);
- 30. Metabolic bone disease (self-report) including history of non-traumatic fracture from a standing height or less and/or current pharmacologic treatment for low bone mass or osteoporosis, other than calcium, vitamin D, or estrogen;
- 31. Hospitalization for COVID-19 infection in the past 12 months; individuals who tested positive for COVID-19 but were not hospitalized must be symptom-free at least 14 days;
- 32. Partial and/or full hysterectomy (self-report);
- 33. Not willing to archive biospecimens for future use;
- 34. Not willing to undergo the microdialysis procedure;
- 35. Participants who fulfill any of the contraindications for MRI including metal implants, devices, paramagnetic objects contained within the body and excessive or metal-containing tattoos;
- 36. Unable to participate in MR assessments due to claustrophobia or physical limitations of equipment tolerances (e.g., MRI bore size) based on investigator's judgment at screening;
- 37. Positive toxicology result from screening;
- 38. The following medication use is exclusionary:
 - Dose change for any chronic-use drug in the last 3 months;
 - Cardiovascular: beta blockers and centrally acting anti-hypertensive drugs, anticoagulants, antiarrhythmics, and antiplatelet drugs (other than aspirin ≤100 mg/day);

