Dual Energy X-Ray Absorptiometry (DEXA)*: DEXA Scans will be performed to measure body fat and estimate muscle mass using a GE Lunar iDXA whole-body scanner. The participant will remove all metal accessories and may be asked to change into a hospital gown. The participant will lie on the DEXA table while the scanner arm emits low energy X-rays as it passes along the body. The scan takes up to 15 minutes and the radiation dose is less than 1 mrem, less than half the average daily radiation dose in America. A urine pregnancy test will be completed on all women of childbearing potential

(all women except those with prior hysterectomy, tubal ligation, or absence of menses for ≥2 years) prior to the DEXA scan for safety.

⁵Maximal Oxygen Consumption: Aerobic fitness will be determined by measuring maximal volume of oxygen consumed (VO_{2max}) during a stationary bicycle exercise test. Provider monitoring will follow The American College of Sports Medicine (ACSM) Guidelines for Exercise Testing and Prescription. During the test, participants will breathe through a low resistance mouthpiece and wear a nose clip. Expired gases will be measured by indirect calorimetry and heart rate/rhythm monitored by 12-lead EKG. Participants will perform an exercise test on a stationary bicycle ergometer (Lode Excaliber, Gronigen, The Netherlands) at the local site. The test will begin with a warm-up of light pedaling. After the 2-minute warm up at a constant workload, the workload will increase in a ramped manner that is individualized to the participant (either 10watts/minute or 15watts/min) based on participant characteristics. VO_{2max} tests will take as little time as possible in order to ensure that test termination is due to the subject reaching VO_{2 max} rather than terminating the test due to muscle exhaustion. There are several additional criteria that will be used to determine if maximal aerobic capacity is achieved. These criteria are the respiratory exchange ratio (RER) increased to 1.05 or higher and the subject's heart rate increased to within 10 beats of the age-predicted maximum (208 – [0.7 x age]). This test will be supervised by a qualified Medical Provider as stated in "TRI SOP 030.100.015 Procedural Staffing.". All study investigators and staff involved in the project are appropriately trained to conduct each element of the research in accordance with standard operating and quality control procedures.

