Dual Energy X-ray Absorptiometry (DEXA): There is a very small risk of cancer with excessive exposure to any radiation. There are also risks for unborn children associated with radiation exposure. The radiation dose from the scan is less than a chest x-ray, or less than half the average amount a person would receive in a day in America.

Magnetic Resonance Imaging: There are no known biological risks associated with magnetic resonance imaging. Some short-term discomfort may be experienced. The short-term risks associated with MRI are minimal, but include heating, loud noises and claustrophobia. There are some people who should not undergo MRI; the contraindication is largely based on the presence of metal objects within a person (i.e. pacemaker, aneurysm clip, metal fragments, etc.).

Maximal Oxygen Consumption (VO_{2max}) test and exercise training: There is a risk of changes to blood pressure, irregular, fast or slow heart rhythm, fainting, and in rare instances (<0.01%) heart attack, stroke, or death with exercise testing, at similar rates to exercising during daily life.

Hair Collection: There is minimal risk associated with obtaining hair samples. A rare risk includes minor scalp laceration during sample collection and related infection.

Adipose Tissue Biopsy: There is a risk of pain from the local anesthesia, and a risk of bruising, bleeding and infection at the site of the biopsy. In addition, there is a risk of skin irritation due to the steri strips and dressing.

Muscle Tissue Biopsy: There is a risk of pain from the local anesthesia, and a risk of bruising, bleeding (hematoma) and infection at the site of the biopsy. In addition, there is a risk of skin irritation due to the steri strips and dressing. Local sensory loss may occur by cutting a subcutaneous sensory nerve (<1 in 100), which is almost always temporary but occasionally can become permanent. On rare occasion (<1 in 1000) bleeding, requiring hospitalization, may occur. The procedures are well tolerated when performed properly.

Intravenous lines/blood draws (lab samples, e.g.): there is a risk of pain, vasovagal syncope, hematomas, and/or infection at IV insertion/blood draw site (low risk of SAE).

Subcutaneous Microdialysis: There is a risk of pain, hematomas, and/or infection at insertion site (low risk of serious AEs).

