Deuterium-labeled water (²H₂O) administration: ²H₂O-labeled water is water that is labeled with the stable, non-radioactive isotope deuterium. Deuterium-labeled water poses minimal health risk associated with drinking it. Participants may rarely experience transient dizziness or nausea following the initial intake.

Hyperinsulinemic-euglycemic clamp: There is the risk of bruising at the site of needle insertion in the veins. The risk of receiving an insulin infusion is that it could produce hypoglycemia (rare). Hypoglycemia may cause one to feel nervous, shaky, sweaty, hungry, and dizzy and have a rapid heart rate. If severe, hypoglycemia can cause coma, seizure or even death (all rare).

Current Version Date: 08/05/2024 IRBNet #: 1805407
Page 31 of 42

Resting Metabolic Rate/Respiratory Quotient (RMR/RQ): There is no physical risk associated with RMR/RQ. Other risks include a feeling of claustrophobia experienced by some subjects while under the transparent "hood".

Surveys: There are no risks involved beyond what would reasonably be encountered in everyday life. It is possible that participants may experience the following during completion of surveys:

- 1. Loss of privacy as a result of a breach of confidentiality
- 2. Undue stress related to content on the survey instruments

Mitigation of Risks

Dual Energy X-ray Absorptiometry (DEXA): A urine pregnancy test will be done prior to scans of all women of childbearing potential (all women except those with prior hysterectomy, tubal ligation, or absence of menses for ≥ 2 years).

Magnetic Resonance Imaging: There will be a strict safety screening protocol, to ensure any people with contraindications are excluded from volunteering.

Incidental Findings: There will be no diagnostic analysis associated with any of the MR sequences used in this protocol. However some of the MR images we obtain as part of this protocol may show incidental medical findings. In the case where a medical abnormality is apparent on an image, the image will first be reviewed by an investigator on this protocol. If the abnormality is confirmed, then the participant will be instructed to seek medical attention from their health care provider.

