Appendix:

The following table identifies the procedures in relation to the study timeline for CTRL group:

	Screen	В	aseline						² H:	2O Inter	vention	Period					F	Follow-	-up	
					Week															
Visits	SV1	V1	V	2	1	2	3	4	5	6	7	8	9	10	11	12	V3	V	4 §	
Days		-14	-8	-7	0-6	7-13	14-20	21-27	28-34	35-41	42-48	49-55	56-62	63-69	70-76	77-83	85	87	88	
Windows	Within 28 days of V1	±2	±2		±1	±1	±1	±1	±1	±1	±1	±1	±1	±1	±1	±1	±1	±1		
Informed Consent	X																			
Eligibility Assessment	X																			
Randomization		X																		
Urine Collection (urea, nitrogen and creatinine)			X															X		
Urine Collection (pregnancy, if applicable)	X	X							X								X			
Urine Collection (toxicology)	X																			
Physical Exam + Medical History	X																			
Vital Signs	X																			
Anthropometrics	X	X															X			
Screening Blood Draw	X																			
Electrocardiogram	X																			
Surveys			X															X		
MRI		X															X			
DEXA		X							X*								X			
VO2max Test		X															X			
Overnight Stay with Standardized Meal			X															X		
7-Day Food Record Start				X												X				
7-Day Food Record Return					X												X			
Hair Collection			X															X		
WAT Biopsy				X															X	
Muscle Biopsy				X															X	
Respiratory Quotient (Hood)				X															X	
Pre-Clamp Blood Draw				X															X	

Hyperinsulinemic-euglycemic Clamp + Microdialysis				X															X
Accelerometer Provided			X													X			
Biopsy and Catheter Insertion Site Check					X														X
On-site Body Weight Measurement							X		X		X		X		X				
Weight Maintenance and Health Education							X		X		X		X		X				
² H ₂ O Pick-up					X		X		X		X		X		X				
² H ₂ O Container Return							X		X		X		X		X	X			
² H ₂ O Urine Collection					X	X	X	X	X	X	X	X	X	X	X	X			
Review Adverse Events	X	X	X	X	X	X	X	X	X	X	X	X	X	X	X	X	X	X	X

^{*}DEXA can take place between Weeks 4-6 to increase scheduling flexibility

On-site Body Weight Measurement, Weight Maintenance and Health Education, and ²H₂O activities must occur on the first day of exercise for that week.

[§]Visit 4 procedures must be done within 36-48 hours after the VO2max test

The following table identifies the procedures in relation to the study timeline for EX group:

The following table identifi	Screen		Baseline						H ₂ O and		_	ention P	eriod				Fo	llow-u	-up
			Week																
Visits	SV1	V1	V	2	1	2	3	4	5	6	7	8	9	10	11	12	V3§	V	7 4

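### The pre-DEXA pregnancy test exempts women without menses for two years or more, an exemption with no valid use in a pre-menopausal cohort

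*Protocol*

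**What the plan says.** The Visit 1 DEXA item (Baseline Period) asks for a urine pregnancy test before the scan in women of childbearing potential, and defines that group as "all women except those with prior hysterectomy, tubal ligation, or absence of menses for ≥2 years". The DEXA entry under Mitigation of Risks repeats the rule and the definition: "A urine pregnancy test will be done prior to scans of all women of childbearing potential".

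Other parts of the protocol bear on who can fall under the exemption:

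- Inclusion criterion 1 admits "Men and pre-menopausal women"; criterion 2 sets the age range at 18-45 years.
- Inclusion criterion 4 applies to women "if not using pharmaceutical (hormonal) contraception (i.e. birth control pills, vaginal ring, injections, or implant" and then lists the acceptable alternatives, tubal ligation among them.
- Exclusion criterion 28 bars current pregnancy and names its check: "pregnancy test performed on day of DEXA scan in women of child-bearing potential".
- Exclusion criterion 32 is "Partial and/or full hysterectomy (self-report").
- Potential Risks, under DEXA, states: "There are also risks for unborn children associated with radiation exposure".

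The Screening Visit also lists a urine pregnancy test, qualified only as being done where applicable, with no definition of when that is.

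**The concern.** An exemption for prolonged absence of menses makes sense where post-menopausal women can enrol, because it serves as a marker that menopause has passed. This trial does not admit post-menopausal women. Anyone who enrols and meets the clause is a pre-menopausal woman of 45 or younger with a uterus, and for her the absence of menses does not establish that she cannot be pregnant.

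Two things depend on the definition. It governs the stated mitigation for a fetal radiation risk that the protocol itself names, and it governs the test that exclusion 28 uses to establish that a participant is not pregnant. The Visit 1 test is also the last one scheduled before the biopsy, the insulin clamp and the start of labelled-water dosing, so a skipped test affects more than the scan. The matter is one of participant safety and eligibility checking, not of estimation or power.

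**Working it through.** The protocol gives no figure to reproduce here. The check crosses each exempt category with the eligibility criteria and then counts the tests affected.

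**Step 1: who can be exempt.**

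| Exempt category | Relevant criterion | Who remains |
|---|---|---|
| Prior hysterectomy | Exclusion 32 bars it | Nobody; redundant but harmless |
| Tubal ligation | Inclusion 4 accepts it as surgical sterility | A consistent exemption; not disputed |
| No menses for 2 years or more | Inclusion 1 bars post-menopausal women; exclusion 32 bars hysterectomy as the cause | Only enrolled pre-menopausal women with a uterus |

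**Step 2: the two readings of the third row.** The protocol does not define pre-menopausal.

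- If a site takes two years without menses to mean not pre-menopausal, the woman fails inclusion 1 and the clause applies to nobody.
- If a site does not, she enrols, inclusion 4 still asks her for contraception or a listed alternative, and the clause releases her from the DEXA-day test.

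Neither reading gives the clause a useful function. No criterion bars amenorrhoea as such. A plausible example is a woman whose menses are suppressed by a hormonal method that inclusion 4 accepts. That such methods can suppress menses is general clinical knowledge and is not stated in the protocol, but the logic of the two readings does not need it.

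**Step 3: tests affected per woman.** Both Appendix schedules place pregnancy urine at screening, Visit 1, the Week 5 column (DEXA allowed in Weeks 4-6) and Visit 3, which makes 4 tests. DEXA falls at Visit 1, the Week 5 column and Visit 3, which makes 3.

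- Tests that the exemption can remove: 3 of 4.
- If the qualifier on the screening test is read by the same definition: 4 of 4.

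**Step 4: how old a screening-only test can be.** The schedule places screening "Within 28 days of V1". Visit 1 is Day -14 (±2) and Visit 3 is Day 85 (±1).

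- Screening to first DEXA: up to 28 days.
- Screening to last DEXA, nominal days: 28 + 14 + 85 = 127 days.
- With Visit 1 two days early and Visit 3 one day late: 28 + 16 + 86 = 130 days.

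**Step 5: tests added by the fix.** The number of affected women is not in the protocol. Assuming 1 to 5 for illustration:

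- DEXA-day tests: 3 × 1 = 3 to 3 × 5 = 15.
- Including screening: 4 × 1 = 4 to 4 × 5 = 20.

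**The case against.** The case for leaving the text alone has several parts.

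- **There is no literal contradiction.** Exclusion 28 promises the test only to women of childbearing potential, and the exemption defines that term, so a woman outside the definition was never promised it. This is correct. The problem is that the definition does not fit the cohort.
- **The affected group may be empty.** Polycystic ovarian syndrome, eating disorders, hyperthyroidism, recent childbirth or lactation, and non-contraceptive estrogens or progestins are all exclusions, which removes several possible causes of long amenorrhoea. The likeliest remaining woman is on a hormonal method and so is already using contraception. This stands, and it limits the size of the point.
- **Other safeguards remain.** Medical history, physical examination, the contraception criterion, the bar on planned pregnancy, review of medical changes during the intervention, and investigator discretion all still apply. This stands too, although none of them is a pregnancy test.
- **The exposure is tiny.** The protocol puts the dose below 1 mrem per scan, less than half an average day's background exposure. This also stands.

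These points lower the importance. None of them identifies a woman in this trial for whom the amenorrhoea exemption would be needed. A rare participant who is infertile for some other reason would at worst give an unnecessary urine sample.

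**Conclusion.** The concern holds as a minor one. In this population the two-year amenorrhoea clause is either empty or releases an enrolled, potentially fertile woman from the pregnancy test on which exclusion 28 and the DEXA risk mitigation rely. For such a woman, 3 of 4 scheduled tests can lapse, or 4 of 4 depending on how the screening qualifier is read. Any screening test that is done may be up to 127 days old at the last scan (130 with windows).

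The conclusion rests on the eligibility criteria as written and on a site not treating two years of amenorrhoea as the end of pre-menopausal status. The counts describe tests that can be skipped, not pregnancies missed. How many women are affected is unknown; few or none is likely. No endpoint, randomisation step or sample-size element is touched.

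**What to change.** In the Visit 1 DEXA item and in the DEXA entry under Mitigation of Risks, remove the two-year amenorrhoea exemption from the definition of childbearing potential. The hysterectomy exemption can go at the same time, since exclusion 32 makes it redundant; that is optional tidying. Tubal ligation then remains as the only exemption.

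Add one line stating that this definition also decides when the screening pregnancy test applies. The same line can cover the pregnancy rows of the two Appendix schedules, although the entries at Visit 1, Week 5 and Visit 3 already fall on DEXA visits governed by the definition.

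The cost is a wording change in two places plus the clarifying line, and at most four extra urine tests per affected woman, all at visits already scheduled.
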